Research Facilities:	UPMC Montefiore Hospital CTRC [name] UPMC Montefiore Hospital Endocrinology and Metabolism Research Center (EMRC) [name]	
Clinical Laboratories:	UPMC Presbyterian University Hospital [name]	

	Pittsburgh, PA 15213
Study Rationale:	Preclinical and clinical research over the last decade has revealed the important vasoprotective effects of nitrites with regards to reduction in blood pressure, vascular inflammation and endothelial dysfunction. New findings suggest an effect of nitrite therapy in the regulation of glucose-insulin homeostasis. Development of an oral formulation of nitrite salts is attractive, whereby nitrite would ensure rapid acting effects upon absorption.
Study Objectives:	To investigate effects of an oral inorganic nitrite on the cardiometabolic and hormonal disturbances observed in a targeted population of overweight/obese adults with metabolic syndrome and hypertension, at risk for insulin resistance and endothelial dysfunction.
Study Hypothesis:	Oral supplementation with nitrite will result in improvement in insulin sensitivity, reduction in blood pressure, and improvement in endothelial and mitochondrial function, arterial stiffening, and microvascular inflammation, in overweight/obese adult subjects with metabolic syndrome and hypertension with limited toxicity in the dose proposed.
Study Aims:	
 1. To examine the effect of oral nitrite on insulin sensitivity and mitochondrial function in overweight/obese adults with metabolic syndrome and hypertension. 2. To examine the effect of oral nitrite on blood pressure in overweight/obese adults with metabolic syndrome and hypertension. 3. To examine the effect of oral nitrite on endothelial function, arterial stiffening, and microvascular inflammation in overweight/obese adults with metabolic syndrome and hypertension.
Study Design:	
The study aims to assess the safety and feasibility of oral nitrite in adults with hypertension and metabolic syndrome.
 
Subjects will undergo a screening visit to determine that eligibility requirements are met. Prior to receiving the study drug, subjects will be scheduled within 4 weeks of screening for a baseline assessment.
 
Subjects who meet the Inclusion Criteria and none of the Exclusion Criteria will be provided study drug. The study population (n=30) will receive oral sodium nitrite for 12 weeks:
 
Drug: oral formulation of sodium nitrite 40 mg three times daily or TID (once in the morning and again in the early afternoon and again in the evening).

	
Subjects will be evaluated as an outpatient with the first dose of study drug. Blood pressure, heart rate, methemoglobin levels and plasma nitrate and nitrite will be measured in the first two hours after dosing. Every other week safety visits will occur to assess adverse events (AE), methemoglobin level, interval histories, brief physical exams, medication compliance review and dispensing of study drug. Interval histories and physical exams will be obtained by a study investigator.
 
Subjects will also be contacted by the study investigator and/or the study coordinator for a follow-up assessment on Week 16 by telephone.

Planned Sample Size:	30 subjects
Duration of Treatment:	12 weeks
Major Inclusion Criteria:	
 • Age 18-60 years • BMI ≥ 30 kg/m² • Hypertension: defined as systolic blood pressure ≥ 130 and/or diastolic blood pressure ≥ 85 mm Hg at screening • Waist circumference: >102 cm in men, >88 cm in women
Major Exclusion Criteria:	
 • Positive urine pregnancy test or breastfeeding • Concurrent use of medications affecting glucose (oral hypoglycemics, insulin, atypical antipsychotics) • Recent addition or change in dosing of hormonal contraceptive medications (OCP, IUD, DepoProvera) • Current use of ≥ 3 anti-hypertensive agents regardless of blood pressure control or normotensive (SBP<130 and DBP<85 mmHg) on a single agent • Current use of PD5 inhibitors or organic nitrates • Not stable on treatments for the prior three months or not planning to remain on current dose of medications for blood pressure, contraception, etc. • Known chronic psychiatric or medical conditions including diabetes, liver or kidney disease or obesity syndromes • TSH >8 mIU/mL • Smoker • Hemoglobin <11 g/dL
Study Endpoints:	
Primary endpoint: Primary outcome measure: change in insulin sensitivity (i.e. insulin stimulated glucose disposal) by hyperinsulinemic euglycemic clamp
 
Secondary endpoints: Secondary outcome measures: 1. Change in systolic, diastolic and mean arterial pressures from baseline to 12 weeks

2. Change in endothelial function by flow mediated dilation (FMD)
3. Change in muscle and platelet reactive oxygen species (ROS) generation, mitochondrial efficiency, and uncoupling in platelet and muscle biopsy sample studies
4. Change in body weight
5. Change in arterial stiffening by carotid-femoral pulse wave velocity (PWV)
6. Change in arterial (intimal) thickening by carotid intima-media thickness (IMT)
7. Change in HbA1C
8. Change in blood markers of inflammation, and vascular dysfunction: ICAM-1, VCAM-1, e-Selectin, CRP, PAI-1, IL-6, TNF- α , lipid profile, adiponectin, and leptin
9. Change in substrate oxidation by indirect calorimetry
10. Change in cardiorespiratory fitness by maximal exercise tolerance test
11. Change in body composition by whole body DEXA for total body fat
12. Safety monitoring with every other week methemoglobin by co-oximetry and plasma nitrate and nitrite concentrations by gas phase ozone-based chemiluminescence detection

1. OBJECTIVE, SPECIFIC AIMS, BACKGROUND, AND SIGNIFICANCE

1.1 OBJECTIVE

The objective of the study is to investigate effects of an inorganic sodium nitrite on the cardiometabolic and hormonal disturbances observed in a targeted population of overweight/obese adults with metabolic syndrome and hypertension, at risk for insulin resistance and endothelial dysfunction.

1.2 SPECIFIC AIMS

Hypothesis:

Oral supplementation with sodium nitrite will result in improvement in insulin sensitivity, reduction in blood pressure, and improvement in endothelial and mitochondrial function, arterial stiffening, and microvascular inflammation, in overweight/obese adult subjects with metabolic syndrome and hypertension with limited toxicity in the dose proposed.

Specific Aims:

Aim 1: To examine the effect of oral nitrite on insulin sensitivity and mitochondrial function in overweight/obese adults with metabolic syndrome and hypertension.

Aim 2: To examine the effect of oral nitrite on blood pressure in overweight/obese adults with metabolic syndrome and hypertension.

Aim 3: To examine the effect of oral nitrite on endothelial function, arterial stiffening, and microvascular inflammation in overweight/obese adults with metabolic syndrome and hypertension.

1.3 BACKGROUND

1.3.1. Insulin Resistance is a Key Link in the Metabolic Syndrome, Type 2 Diabetes & Cardiovascular Disease

Insulin resistance (IR) within muscle is a significant risk factor for the development of T2DM^{1,2} and CVD³. Weight loss and exercise are effective treatments of IR⁴, but compliance and adherence are typically poor. There are effective pharmacologic therapies, e.g., PPAR γ receptor agonists (Rosiglitazone), but there are significant side effects. More effective targeted approaches to improve IR would therefore have a major impact on the prevention and treatment of both diabetes and CVD. The potential link between impaired mitochondria function and skeletal muscle IR has been extensively investigated and is disputed^{5,6}. In addition, H₂O₂ emission from skeletal muscle mitochondria is an important marker of the balance between oxidative stress and redox state and is associated with IR independently of mitochondrial energy production⁷.

1.3.2. Cardiovascular Disease and Inorganic and Dietary Nitrates and Nitrites

Cardiovascular disease remains the leading cause of death in the United States and worldwide¹. While several large studies including the landmark Dietary Approaches to Stop Hypertension (DASH) study demonstrated that fruit and vegetable rich diets significantly reduced blood pressure²⁻⁴ and reduced the risk of ischemic stroke⁵ and cardiovascular disease in general⁶, the exact mechanisms remain poorly understood. A new theory is

focusing on dietary nitrate and endogenous nitrite as major players in the cardiovascular protection seen in fruit and vegetable-rich diets. In humans, two major sources of nitrate and nitrite exist in the body: diet and endogenous production from the L-arginine-NO synthase pathway⁷. Green leafy vegetables and beetroots are rich dietary sources of nitrates (NO_3^-). When ingested, they are chemically stable endogenous reservoirs of nitric oxide (NO) and are reduced to nitrites (NO_2^-) by oral bacterial flora in the saliva. Next, the nitrites are swallowed entering the GI tract and accumulate via the enterosalivary circulation pathway. While the classical pathway of vasoprotective NO production predominates from oxidation of L-arginine by endothelial NOS (eNOS) activity, nitrites in the vasculature can also be reduced to generate NO via a reverse or “alternate” pathway under conditions of acidosis and hypoxia. This theory is evidenced by human studies and animal models demonstrating that inorganic and dietary nitrates and nitrites have robust NO-signaling effects. These effects include maintaining basal vascular tone, decreasing blood pressure (BP) by vasodilation, reducing vascular inflammation, preventing endothelial dysfunction and inhibiting platelet aggregation^{8,9}. Very recent animal studies suggest nitrates and nitrites may also positively impact blood glucose and insulin sensitivity¹⁰. Thus, a novel therapeutic strategy targeting the cardiometabolic mechanisms underlying metabolic syndrome and hypertension may lie in the nitrate-nitrite-NO pathway.

1.3.3. Effects of Nitrite/Nitrate on Blood Pressure

Currently, several human studies have examined the effect of single ingestion^{11,12}, 6 day^{13,14} and 15 day¹⁵ supplemental courses of nitrate in the form of beetroot juice on blood pressure in healthy adults. Systolic¹¹⁻¹⁵ (SBP), diastolic^{11,14,15} (DBP) and mean arterial pressures^{11,14,15} (MAP) were significantly reduced with beetroot juice in these trials. A traditional Japanese diet is another rich source of dietary nitrates and short term evaluation of this diet in healthy Japanese adults decreased DBP 4.5 mmHg in comparison to a low nitrate control diet ($p=0.0066$) without a change in SBP¹⁶. Single administration of inorganic potassium nitrate¹² in various mmol concentrations or 3 days of sodium nitrate¹⁷ significantly reduced SBP¹², DBP^{12,17} and MAP¹⁷ in healthy adults compared to placebo, with the magnitude of the blood pressure (BP) reduction related to the baseline BP¹². Sex differences in the reduction of SBP ($p<0.01$) and DBP ($p<0.001$) were also identified and greater in males than females¹². Single administration of oral and intravenous 0.12mmol sodium nitrite solution/mmol hemoglobin in healthy adults, equivalent to 290-380 mg sodium nitrite, resulted in a median decrease in MAP of 11 and 14 mmHg, respectively. A compensatory increase in HR of 10 and 18 bpm, respectively, was observed¹⁸. To our knowledge, the effect of longer courses of dietary or inorganic nitrate and nitrite supplementation on blood pressure, particularly in at-risk patients, has not been investigated.

1.3.4. Effects of nitrite/nitrate on glucose-insulin homeostasis

The PPAR γ receptor is known to regulate glucose uptake, lipid metabolism/storage and cell proliferation/differentiation. Potential benefits of a particular drug in the class targeting this receptor, rosiglitazone, has been touted, but with an increased risk for adverse cardiovascular events¹⁹. In contrast, nitro-fatty acids, endogenous products of nitric oxide and nitrite-mediated redox reactions, were shown in a recent study to act as partial PPAR γ receptor agonists with profiles distinct from rosiglitazone and activate the PPAR γ receptor at nanomolar concentrations¹⁰. In the same paper, obese diabetic insulin resistant ob/ob mice were treated with nitro-fatty acids by subcutaneous pump for 4 weeks with reduction of insulin plus normalized blood glucose levels, ie. improvement of insulin sensitivity, without the side effect of weight gain seen with rosiglitazone. A recent animal study examined the effects of dietary supplementation of inorganic nitrate on various features of metabolic syndrome in mice lacking the gene for endothelial NO synthase (eNOS)²⁰. These mice are obese, hypertensive, insulin resistant and have dyslipidemia, much like humans with metabolic syndrome or a polymorphism in the eNOS gene. With chronic (10 weeks) nitrate treatment in eNOS -/- mice,

significant reductions in blood pressure, fasting blood glucose, HbA1C, proinsulin to insulin ratio, visceral fat, circulating triglycerides, and body weight were demonstrated. To our knowledge, however, no human data is available on the effects of inorganic nitrate or nitrite supplementation on insulin sensitivity, especially in an adult overweight/obese population with metabolic syndrome and hypertension.

1.3.5. Effects of nitrite/nitrate on endothelial function and vascular inflammation

One of the earliest pathophysiological responses to cardiovascular injury is a reduction in NO bioavailability. This has been implicated in the resulting endothelial dysfunction, inflammation, platelet activation, and smooth muscle proliferation and migration⁹. Recent evidence has suggested the alternate NO pathway involving nitrate and nitrite may attenuate arteriolar endothelial dysfunction and microvascular inflammation through increased NO bioavailability. Stokes and colleagues fed male C57 mice for 3 weeks with either a high fat or normal diet. Those mice on the high fat diet were supplemented with nitrite free or nitrite containing water. Nitrite supplementation with high fat feeding significantly increased plasma and tissue nitrite levels, inhibited leukocyte adhesion and emigration in venules and prevented impairment of endothelium-dependent vascular relaxation while MAP remained unchanged. Additionally, nitrite supplementation was associated with a reduction in triglycerides ($p < 0.01$) and CRP without altering total cholesterol⁹. In human models, dietary nitrate in the form of beetroot juice^{11,12} and inorganic nitrate supplementation¹² prevented I/R-induced endothelial dysfunction ($p < 0.05$) assessed by FMD when compared to no treatment. Collectively, evidence from these animal models and human studies suggest a potential therapeutic role of exogenous nitrates and nitrites to enhance NO bioavailability, reduce microvascular inflammation, and preserve endothelial function.

1.3.6. Effects of nitrite/nitrate on mitochondrial function

Mitochondria are critical for oxidizing fuels (i.e., glucose, fatty acids, amino acids) for cellular energy production. There is also accumulating evidence that mitochondria dysfunction is associated with insulin resistance within skeletal muscle^{21,22}. Larsen et al recently reported in healthy volunteers that dietary inorganic nitrate supplementation increased ATP synthesis in mitochondria isolated from muscle biopsy specimens concomitant with a reduced whole-body oxygen cost during steady-state exercise²³. This suggests that dietary nitrate enhances the efficiency of energy generation through direct effects on muscle mitochondria. Taken together, these studies raise important questions regarding the potentially positive benefits of inorganic nitrate and nitrite supplementation on mitochondrial energy metabolism and links with insulin resistance and the metabolic syndrome. The current study will extend these observations significantly by examining the effects of dietary nitrate/nitrite supplementation on energy efficiency, mitochondria function, oxidative stress and insulin resistance in subjects with key features of insulin resistance and the metabolic syndrome.

1.4 SIGNIFICANCE

Important vasoprotective effects of inorganic nitrates and nitrites have been reported during the past decade, as evidenced by reduced BP, vascular inflammation and endothelial dysfunction. More recent findings suggest that inorganic nitrate and nitrite therapy may be involved in the regulation of glucose-insulin homeostasis. This proposal hypothesizes that oral supplementation with sodium nitrite will result in improvement in insulin sensitivity, reduction in BP, and improvement in endothelial and mitochondrial function, arterial stiffening, and microvascular inflammation, in overweight/obese adult subjects with metabolic syndrome and hypertension with limited toxicity in the dose proposed. First, we utilize a combination of powerful *in vivo* techniques (hyperinsulinemic euglycemic clamp, pharmacokinetic testing, muscle biopsy and platelet

analysis of mitochondrial function, cardiorespiratory fitness and various vascular function studies). Second, this is the first human study to investigate the inorganic nitrate or nitrite effects (in any form) on insulin sensitivity in any subject population. Additionally, this study is the first to design inorganic nitrite capsules for cardiovascular applications.

This study is an open-label, single-center non-randomized drug treatment study of overweight adults with metabolic syndrome and hypertension.

Adults (N=30) who fulfill the inclusion and exclusion criteria will be treated with 40 mg ¹⁴N sodium nitrite three times daily or TID (once in the morning and again in the early afternoon and again in the evening).

2. RESEARCH DESIGN AND METHODS

2.1 CLASSIFICATION AND METHODOLOGICAL DESIGNS

The study is a 12 week open-label, single-center, non-randomized drug treatment study of overweight adults with metabolic syndrome and hypertension.

2.2 DETAILED DESCRIPTION OF STUDY DESIGN

Potential subjects will undergo a screening visit to determine that eligibility requirements are met prior to being enrolled in the study. Subjects who meet the Inclusion Criteria, none of the Exclusion Criteria, and prior to receiving the study drug will be scheduled within 4 weeks of screening for baseline assessments. The study population (n=30) will receive oral sodium nitrite as follows:

Drug: oral formulation of sodium nitrite 20 mg or 40 mg capsules, for a dose of 40 mg three times daily or TID (once in the morning and again in the early afternoon and again in the evening).

Subjects will complete a 12-week outpatient treatment period. During the treatment period, subjects will be evaluated at weekly intervals. Throughout the study period, subjects will be asked to remain diligent in recording the exact date and time of study drug dosing with any associated symptoms.

2.2.1. Study Drug Preparation and Distribution

The nitrite formulation will be prepared at and obtained from the Investigational Drug Pharmacy Service at the National Institutes of Health (NIH-IDS). The University of Pittsburgh Medical Center Investigational Drug Pharmacy Service (UPMC-IDS) will be utilized for dispensing of the study drug.

The daily study drug is:

¹⁴N Sodium nitrite

Standard sodium nitrite will be supplied as 20 or 40 mg capsules for three times daily oral administration at the dose strength of 40 mg.

2.2.2. Dose Selection

The Joint Food and Agriculture Organization (FAO)/World Health Organization (WHO) Expert Committee on Food Additives (JECFA) proposed an Acceptable Daily Intake (ADI) for nitrate in 1990 based on harmless daily intakes of ≤ 500 mg of sodium nitrate/per kg of body weight in rats

and dogs. They divided this dose by an uncertainty factor of 100 to yield an ADI of 5 mg of sodium nitrate or 3.7 mg nitrate ion per kg of body weight. An ADI for nitrite ion was derived and revised in 2003 based on intakes of 10 mg of sodium nitrite or 6.7 mg nitrite ion per kg of body weight in rats. They divided this dose by an uncertainty factor of 100 and rounded to yield an ADI for sodium nitrite of 0.1 mg/kg of body weight²⁴.

Using the ADI for sodium nitrite (0.1 mg/kg of body weight) and a body weight of 95 kg, the calculated ADI of sodium nitrite would be 9.5 mg.

A recent modeling of the fruit and vegetable consumption patterns of The Dietary Approaches to Stop Hypertension (DASH) diet was done choosing foods that were low or high in nitrate. The “high nitrate” DASH diet pattern would result in consumption of 1,222 mg nitrate ion and 0.351 mg nitrite ion daily. The “low nitrate” DASH diet would result in consumption of 174 mg nitrate ion and 0.41 mg nitrite ion daily. The hypothetical high-nitrate DASH diet pattern exceeds the WHO’s ADI for nitrate ion by 550% for a 60-kg adult²⁶. Subjects on this diet exhibited lower blood pressure with no adverse effects.

In a recent study¹², single dose potassium nitrate (KNO₃) capsule ingestion in healthy adult volunteers in doses of 2,424 mg KNO₃ (or 1,488 mg nitrate) and 1,212 mg KNO₃ (or 744 mg nitrate) resulted in dose dependent reductions in BP over a 24 hour period without adverse effects.

Hunault et al. reported an open-label pharmacokinetic crossover study in 9 healthy adult subjects who received two single high dose oral sodium nitrite solutions equivalent to 290-380 mg and 140-190 mg sodium nitrite, respectively, and one intravenous sodium nitrite dose of 290-380 mg¹⁸. Mild headache occurred in 44-55% and up to 22% experienced nausea, which subsided within half an hour during each treatment session. Lowered blood pressure accompanied by increased heart rate were observed after each higher dose treatment, whereas the lower dose did not induce notable changes.

Chronic dietary supplementation of inorganic sodium nitrate in obese, hypertensive, insulin resistant mice lacking the gene for endothelial NO synthase (eNOS)²⁰ was studied. With a 10 week treatment of a modest dose of sodium nitrate of 0.1 mmol/kg/day (8.5 mg/kg/day) in the drinking water, significant reductions in blood pressure, fasting blood glucose, HbA1C, and proinsulin to insulin ratio were demonstrated, indicating reduced demands on the β-cell for insulin secretion.

Sodium nitrate drug is considered a source of nitrite through salivary nitrate reduction (rise in plasma nitrite after single oral sodium nitrate dose - see attached Fig 2A attached). Despite the plasma nitrite rise following a single oral sodium nitrate dose, we recently demonstrated in our phase I PK/PD study in 10 normal volunteers that no persistent blood pressure reduction with sodium nitrate 1,000 mg (see attached Fig 3A). In contrast, in the same phase I PK/PD study in 10 normal volunteers, we showed blood pressure decline in systolic, diastolic and mean arterial pressures over 3 hours with sodium nitrite 20 mg (Fig 3B). The oral sodium nitrite half-life was about 40-minutes and the effects of nitrite only lasted ≤6 hours. This was demonstrated by the plasma nitrite levels returning to baseline levels between 3 and 6 hours after nitrite dosing (i.e. the drug was given and gone out of the circulation within 6 hours). Specifically, mean baseline (pre-nitrite dosing) blood nitrite concentrations were 0.11 micromolar with a peak at 30 minutes of 5.5 micromolar, and return to baseline levels between the 3- (0.18 micromolar) and 6-hour (0.11 micromolar) monitoring time points (Fig 2B). In addition, there were no serious adverse events when these normotensive individuals received sodium nitrite including our 2 safety endpoints of methemoglobin levels and mean arterial pressure.

Additionally, we demonstrate lack of blood pressure lowering in our first 5 subjects on this current protocol's combined regimen of sodium nitrate 1,000 mg daily and sodium nitrite 20 mg BID during 2-hour post-dose BP monitoring at baseline vs. 12 weeks post (see attached Fig 1A), weekly seated blood pressures (Fig 1B) or 24-hour ambulatory blood pressures (ABP) at baseline vs. 12 weeks post (Fig 1C) and possible concern the sodium load within the 1,000 mg sodium nitrate dose may be blunting any potential BP effect.

Next, a recently published study (Mohler III ER, Hiatt WR, Gornik HL, Kevil CG, Quyyumi A, Haynes WG, Annex BH. Sodium nitrite in patients with peripheral artery disease and diabetes mellitus: safety, walking distance and endothelial function. *Vascular Medicine* 2014; 19(1):10-17) randomized adults 1:1:1 to oral sodium nitrite 40 mg BID vs. 80 mg BID vs. placebo for 10 weeks in >50 adults (age 35-85 years) with peripheral arterial disease +/- diabetes. The dose was escalated after the 10 weeks for 1 additional week in all 3 groups (dose-doubling) to 80 mg BID vs. 160 mg BID vs. doubling of placebo, respectively. The dosing was well tolerated, especially in the 40 mg BID and 80 mg BID randomized dosings. Our proposed study dosing of 40 mg TID (120 mg daily) falls in between the above two total daily doses of 80 mg and 160 mg daily. Safety was monitored throughout all aspects of the study. No serious adverse events occurred in the two sodium nitrite groups. There were no imbalances in GI, musculoskeletal, respiratory, vascular or skin disorders nor shifts in liver function or creatinine levels. Pertinent safety outcomes (also measured in our study) revealed that methemoglobin changes never exceeded 3% in any nitrite dose regimen and no clinically significant change in resting blood pressure.

Finally, a current phase II study of inhaled nitrite in patients with pulmonary arterial hypertension (PAH) at the University of Pittsburgh uses a dose of 80 mg, and is approved by the University of Pittsburgh IRB and FDA. Also, phase II studies went as high as 90 mg three times a day, approved by the FDA. So, our dose of 20 mg or 40 mg TID will not be out of line of approved dosing.

Based on the above PK and the differential BP effects with single doses of sodium nitrate vs. nitrite, the published 10-week oral nitrite trial and preliminary findings in this combined trial, we propose to remove sodium nitrate, which is the second potential depot of nitrite. Therefore, we need to administer a greater nitrite load since the previous two sources combined (sodium nitrate and nitrite) in the first 5 subjects of this study did not result in any BP lowering (Fig 1A-C). Similar to our prior dosing modification (when we titrated from sodium nitrite 20 mg once daily to 20 mg twice daily), we propose a step-up dosing in the first 3 subjects enrolled whereby we will begin with sodium nitrite 20 mg TID daily and after 2 weeks on this dosing and if no SAE, increase to 40 mg TID for the remaining 10 weeks of the study, given the PK of the drug and to induce blood pressure lowering in our hypertensive subjects. After three subjects have completed this regimen, then we propose that from the start, all remaining subjects start on sodium nitrite 40 mg TID and continue for all 12 weeks.

Although we are increasing the dose/frequency of sodium nitrite, since we are discontinuing sodium nitrate (which is reduced to nitrite in our body as was confirmed in our Phase I PK study), we are continuing our in-person safety monitoring visits to assess for adverse events at every other week. We will continue alternating every other week phone visits to assess compliance and for adverse events. Our two safety outcomes are methemoglobin by non-invasive co-oximetry and mean arterial pressure (MAP) obtained through 3 automated resting BP measurements 30-45 min following morning nitrite dosing and averaging the final 2 of 3 MAPs.

Based on the Joint FAO/WHO ADI for sodium nitrate and nitrite, the above DASH diet patterns, and the recently observed human and rodent effects of nitrate and nitrite on blood pressure and

glucose homeostasis, including our PK/PD trial of single doses of oral nitrate and nitrite, the existing inhaled nitrite trial, and this open label trial safety and lack of BP reduction findings following a total of 5 subjects' completion, the study investigators believe that a safe and likely therapeutically effective dose of sodium nitrite will be 40 mg three times daily (~1.26 mg/kg body weight per day for a 95 kg subject). Our sodium nitrite dose selection is equivalent to 12.6 times the ADI.

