2.3.2. Treatment Period and Monitoring

Visit 4 (Day 1: First Drug Dose Visit)

Administration of the first dose of study drug will occur within 1-4 weeks following completion of all baseline assessments. Subjects will be asked not to drink or eat anything other than plain water for 8 hours prior to their arrival for this visit. The fasting visit will take place in the outpatient CTRC.

- Body weight and temperature in all subjects and menstrual history in females
- Urine pregnancy test in females of child-bearing potential (i.e. women who are not at least 1 year post-menopausal or who have not undergone a surgical sterilization procedure)
- Subjects will receive their first dose of study drug as follows:
 - ^{14}N sodium nitrite 40 mg
- Blood pressure, MAP and heart rate will be measured in triplicate after approximately 30 minutes of rest and quiet in the CTRC to ensure blood pressures are at a steady state before taking the study drug (baseline) and then every 15 minutes for the 2 hours post-drug administration
- Methemoglobin level by finger probe at 0 (trough prior to sodium nitrite), 0.5, 1 and 2 hours post-drug administration

- Research blood samples for: plasma nitrate and nitrite concentrations, red cell iron-nitrosyl-hemoglobin and platelet studies at 0 (trough), 0.5 and 2 hours post-drug administration
- AE assessment
- Light breakfast snack
- Provide dosing diary cards and a 11-17 day supply of study drug so there is enough daily drug to get them to their next scheduled Visit 6
- Return completed 72 hour dietary recall forms

The total volume of blood drawn is approximately 3 Tablespoons (or 48 mL).

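### Section 2.2.2 starts the first three subjects at 20 mg TID for two weeks, but the Visit 4 instruction gives every subject 40 mg as the first dose

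*Combined protocol and SAP*

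**What the plan says.** Section 2.2.2 (Dose Selection) sets a step-up for the first three subjects enrolled: "begin with sodium nitrite 20 mg TID daily and after 2 weeks on this dosing and if no SAE, increase to 40 mg TID", with the higher dose kept for the remaining 10 weeks. Once three subjects have completed this, everyone else is to start at 40 mg TID and stay there for 12 weeks. Section 5.1.1 also describes the study dose as 20 mg stepping up to 40 mg, without limiting this to three subjects.

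The Visit 4 (Day 1) procedure in section 2.3.2 reads "Subjects will receive their first dose of study drug as follows" and then lists "sodium nitrite 40 mg". It makes no exception for the first three subjects. The same list has staff dispense an "11-17 day supply of study drug so there is enough daily drug to get them to their next scheduled Visit 6".

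The summary statements also give one dose for all. The synopsis has "oral formulation of sodium nitrite 40 mg three times daily or TID" for n=30, section 1.4 has "Adults (N=30) who fulfill the inclusion and exclusion criteria will be treated with 40 mg" (TID), and section 2.2 has "for a dose of 40 mg three times daily or TID". Section 2.2.1 provides for both strengths: "Standard sodium nitrite will be supplied as 20 or 40 mg capsules".

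The step-up condition in 2.2.2 is the absence of an SAE. The numerical limits stand elsewhere, in the stopping rule of section 5.4.2: methemoglobin above 5%, or MAP below 55 mmHg (for a subject whose baseline MAP is below 60, a fall of 20% or more).

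**The concern.** Two current parts of the protocol give different first doses to the same three people. Section 2.2.2 explains and proposes; Visit 4 is the page that is followed on the day. A coordinator or pharmacist working from Visit 4 would have no prompt to look for an exception. Whichever dose is given departs from some part of the text.

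What would be lost is the sponsor's own precaution. Section 2.2.2 introduces the lead-in because the nitrite load is being raised. Prior experience in this protocol was five subjects on nitrite 20 mg BID with sodium nitrate 1,000 mg daily.

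A lesser point concerns the step-up condition. It does not expressly name the two limits that the protocol uses as its safety outcomes, and the SAE definition in section 5.4.5 does not list them.

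**Working it through.** **Reproducing the plan's own figure.** Inputs: 40 mg TID, 95 kg, and an ADI of 0.1 mg/kg for sodium nitrite (section 2.2.2).

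- Daily dose: 3 × 40 = 120 mg
- Per kg: 120 / 95 = 1.26 mg/kg/day
- Multiple of the ADI: 1.263 / 0.1 = 12.6

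These match the approximately 1.26 mg/kg/day and 12.6 times the ADI in section 2.2.2.

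**The lead-in dose on the same basis.**

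- Daily dose: 3 × 20 = 60 mg
- Per kg: 60 / 95 = 0.63 mg/kg/day
- Multiple of the ADI: 0.632 / 0.1 = 6.3

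**The two readings for one of the first three subjects.**

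| | Section 2.2.2 | Visit 4 as written |
|---|---|---|
| First dose | 20 mg | 40 mg |
| Days 1–14 | 60 mg/day | 120 mg/day |
| Days 15–84 | 120 mg/day | 120 mg/day |
| 12-week total | 60 × 14 + 120 × 70 = 9,240 mg | 120 × 84 = 10,080 mg |

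The difference is 60 mg/day × 14 days = 840 mg per subject. The step-up total is 9,240 / 10,080 = 92% of the other. The share of subjects affected is 3 / 30 = 10%.

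**Effect on the primary endpoint.** The second clamp is at Visit 18, in week 12. Under either reading these subjects are scheduled to be on 40 mg TID by then, so the pre-post comparison is barely touched. The sample size calculation in section 2.6 uses no dose input.

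**Monitoring under either reading.** Visit 4 measures blood pressure and MAP every 15 minutes for two hours, and methemoglobin at 0, 0.5, 1 and 2 hours. This applies whatever dose is given.

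**What the protocol does with a breach on 20 mg.** Section 2.3.2 discontinues a subject who still has high methemoglobin or low blood pressure on the lower dose, and section 5.4.2 says the same for each limit. Section 2.3.2 also makes the Visit 5–15 schedule conditional on no dose-limiting event defined by MAP and methemoglobin. The reduction rule itself is written only from 40 mg to 20 mg. How a first breach in someone who started on 20 mg affects the step-up therefore has to be inferred.

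**The case against.** The strongest reply is that a specific rule governs a general one. Section 2.2.2 names the three subjects, the dose, the duration and the hand-over to 40 mg. The synopsis, 1.4 and 2.2 merely summarise the target regimen. That stands for those three places: they need a cross-reference and should not be counted as three further contradictions. It does not rescue Visit 4, which is an operative instruction addressed to all subjects.

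Second, section 2.2.2 reads as the rationale for a dosing change, and the three lead-in subjects may already have been treated when this text applied. If so, 40 mg at Visit 4 is right for everyone remaining. The documents do not settle this, so the harm is conditional. The mismatch in wording is not.

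Third, 40 mg is unlikely to do harm. Section 2.2.2 reports that methemoglobin changes never exceeded 3% in any regimen of a 10-week oral nitrite trial whose lowest active dose was 40 mg BID, with no clinically significant change in resting blood pressure. Section 5.1.1 reports no level above 3% at doses under 75 mg in 80 volunteers. This stands and limits the weight of the point.

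A reader might infer that a subject could be escalated to 40 mg despite a methemoglobin or MAP breach. The documents do not support that. Sections 2.3.2 and 5.4.2 discontinue a subject with a confirmed breach on the lower dose, and criterion 4 of the SAE definition lets the investigator class an important medical event as serious. A reader might also infer that the Visit 6 window or the Visit 4 supply cuts the lead-in short. Section 2.2.2 sets two weeks without tying them to Visit 6, and the supply is sized to last until that visit.

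**Conclusion.** The conflict between section 2.2.2 and Visit 4 is real and should be corrected. Followed as written, Visit 4 doubles the starting dose for three subjects (120 instead of 60 mg/day for 14 days) and removes the lead-in. It does not remove monitoring, and it has a negligible effect on the primary analysis. The size rests on the planned 30 subjects, the protocol's 95 kg, and the assumption that the three have not yet been dosed. The documents do not support the inference that these subjects actually received 40 mg first. Naming the thresholds in the step-up condition is a clarification and repairs no open safety gap.

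**What to change.** 1. At Visit 4, state: *The first three subjects receive 20 mg at this visit and 20 mg TID for 14 days; all subjects enrolled after these three complete the step-up regimen receive 40 mg.* Add a cross-reference to section 2.2.2 in the synopsis, 1.4 and 2.2.
2. For these three, hold Visit 6 no earlier than Day 15 and dispense enough 20 mg capsules to reach it. Give the first 40 mg dose in clinic at Visit 6, not at home. That visit already includes three blood pressure and MAP readings from half an hour after dosing, and methemoglobin by co-oximetry; the co-oximetry should be done after the 40 mg dose.
3. In section 2.2.2, word the step-up condition as: *no SAE and no methemoglobin or MAP threshold breach (section 5.4.2) on 20 mg TID.*
4. If the three subjects have already been treated, say so and state the dose each received.

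The cost is a few sentences in one amendment. Both capsule strengths are already supplied, and sample size and analysis do not change. The downside is a narrower Visit 6 window for three subjects: Day 15 to 22 instead of Day 8 to 22 (Day 15 ± 7 in Table 1). If Visit 6 falls after Day 15, the subject should stay on 20 mg TID until it takes place. If it falls after Day 18, the supply must exceed the 17 days now allowed at Visit 4.
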